10.5 Statistical considerations

The key exploratory HRQoL endpoint relevant for this study is the global health/QoL scale. The following sub-scales and single items will be considered as supportive exploratory HRQoL endpoints: pain, fatigue, appetite loss, shortness of breath, cough, chest pain and dyspnea symptom scales. The other available scales will be classified as "other" exploratory analyses; the financial difficulties scale will not be presented.

The global health/QoL scale will be used as primary outcome of interest for this study. A difference of 10 points on the 100-point QLQ-C30 scale either within a patient or between the two arms will be considered as clinically relevant [Ref. 78]. The standard deviation of this scale is approximately 20 points. With the 2-sided alpha set at 5% and a power of 80% to detect a difference of 10 points (effect size of 0.5), a minimum of 128 patients (64 per treatment arm) is required. For an effect size of 0.75 (difference of 15 points), 56 patients (28 per treatment arm) are required. Therefore, this study is sufficiently powered to detect differences in HRQoL.

Data will be scored according to the algorithm described in the EORTC scoring manual. All scales and single items are scored on categorical scales and linearly converted to 0-100 scales.

Changes in HRQoL scores from baseline per time point will be evaluated by classifying them according to the 10 point change threshold into 3 categories: improved/stable/deteriorated. Patients without a valid HRQoL outcome at a certain time will be considered as having deteriorated at that time. For each patient the proportion of assessments spent in a deteriorated state will be calculated and compared between treatment arms using a non-parametric rank order test in the intent-to-treat population of the whole population and in the PD-L1 strong positive subgroup.

In order to assess the robustness of the results, the following sensitivity analyses will be performed:

- ◆ a clinical relevant threshold of 5 and 15 points will be used and patients without a valid HRQoL score will be classified according to the reported reason for non-compliance.
- ◆ If adequate compliance available, patients will be classified on valid HRQoL score received after treatment discontinuation only.
- ◆ The area-under-the-curve (AUC) will be calculated for each patient based on the global health/QoL scores. Missing values will be considered as 0.

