2. Do you have any trouble taking a long walk?	1	2	3	4
3. Do you have any trouble taking a short walk outside of the house?	1	2	3	4
4. Do you need to stay in bed or a chair during the day?	1	2	3	4
5. Do you need help with eating, dressing, washing yourself or using the toilet?	1	2	3	4
During the past week:				
	Not at All	A Little	Quite a Bit	Very Much
6. Were you limited in doing either your work or other daily activities?	1	2	3	4
7. Were you limited in pursuing your hobbies or other leisure time activities?	1	2	3	4
8. Were you short of breath?	1	2	3	4
9. Have you had pain?	1	2	3	4
10. Did you need to rest?	1	2	3	4
11. Have you had trouble sleeping?	1	2	3	4
12. Have you felt weak?	1	2	3	4
13. Have you lacked appetite?	1	2	3	4
14. Have you felt nauseated?	1	2	3	4
15. Have you vomited?	1	2	3	4
16. Have you been constipated?	1	2	3	4

Please go on to the next page

During the past week:	Not at All	A Little	Quite a Bit	Very Much
17. Have you had diarrhea?	1	2	3	4
18. Were you tired?	1	2	3	4
19. Did pain interfere with your daily activities?	1	2	3	4
20. Have you had difficulty in concentrating on things, like reading a newspaper or watching television?	1	2	3	4
21. Did you feel tense?	1	2	3	4
22. Did you worry?	1	2	3	4
23. Did you feel irritable?	1	2	3	4
24. Did you feel depressed?	1	2	3	4
25. Have you had difficulty remembering things?	1	2	3	4
26. Has your physical condition or medical treatment interfered with your family life?	1	2	3	4
27. Has your physical condition or medical treatment interfered with your social activities?	1	2	3	4
28. Has your physical condition or medical treatment caused you financial difficulties?	1	2	3	4

For the following questions please circle the number between 1 and 7 that best applies to you

29. How would you rate your overall health during the past week?

1 2 3 4 5 6 7

Very poor Excellent

30. How would you rate your overall quality of life during the past week?

1 2 3 4 5 6 7

Very poor Excellent

© Copyright 1995 EORTC Quality of Life Group. All rights reserved. Version 3.0

Health Questionnaire

English version for the UK

(Validated for Ireland)

By placing a tick in one box in each group below, please indicate which statements best describe your own health state today.

Mobility

- I have no problems in walking about
- I have some problems in walking about
- I am confined to bed

Self-Care

- I have no problems with self-care
- I have some problems washing or dressing myself

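### On the key HRQoL scale, the 15-point sensitivity threshold classifies every valid assessment exactly as the 10-point main threshold does, so no stricter definition of change is tested

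*Combined protocol and SAP*

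**What the plan says.** Section 10.5 of the combined protocol and SAP states that "The key exploratory HRQoL endpoint relevant for this study is the global health/QoL scale". On scoring it says: "All scales and single items are scored on categorical scales and linearly converted to 0-100 scales". Change from baseline at each time point is analysed by "classifying them according to the 10 point change threshold into 3 categories: improved/stable/deteriorated", and the main rule for missing forms is: "Patients without a valid HRQoL outcome at a certain time will be considered as having deteriorated at that time". Each patient's share of assessments in the deteriorated state is then compared between arms with a rank test.

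The first listed sensitivity analysis has two parts in one bullet. In the first part the threshold varies: "a clinical relevant threshold of 5 and 15 points will be used". In the second part missing forms no longer all count as deteriorated; instead, "patients without a valid HRQoL score will be classified according to the reported reason for non-compliance". The other items are a classification restricted to scores after treatment discontinuation, an area under the curve, and a graph of change from baseline. All are repeated on the secondary HRQoL scales.

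The QLQ-C30 form in Appendix E introduces the two global items with "For the following questions please circle the number between 1 and 7 that best applies to you". They are question 29, "How would you rate your overall health during the past week", and question 30, the same for overall quality of life. Questions 1 to 28 have four response levels. The documents do not mention the step size of any converted score.

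**The concern.** Varying the cut-off on both sides of 10 is meant to show whether the HRQoL conclusion depends on what counts as a relevant change. That works only if some patients can fall between the cut-offs. A scale built from a few categorical items takes few values, and a threshold moved within a gap between them changes nothing.

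If that happens on the key scale, agreement between the 10- and 15-point classifications is fixed before any data are seen. A report that the result is robust to a stricter definition would then carry no information. There is also an attribution problem. The missing-form rule changes in the same bullet, so a difference produced by that rule could appear under a threshold label.

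**Working it through.** **The plan's own figures.** Section 10.5 sizes the HRQoL comparison for mean differences of 10 and 15 points with SD 20, two-sided 5% and 80% power, and gives 64 and 28 per arm. With n = 2(1.96 + 0.842)²/(d/SD)², 10 points gives 62.8, so 63 per arm, and 15 points gives 27.9, so 28. The t-test version gives 64 and 29. The stated figures are reproduced to within one patient per arm. They concern between-arm means, which are not tied to a grid. The point here concerns only the within-patient classification.

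**Inputs.** Two items rated 1-7 (Appendix E); linear conversion to 0-100, main threshold 10, sensitivity thresholds 5 and 15 (Section 10.5). Assumption: the scale is the equally weighted mean of questions 29 and 30. The scoring manual is cited but not included.

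**Step size on global health/QoL.**
- Score = (mean − 1)/6 × 100 = (Q29 + Q30 − 2)/12 × 100.
- The sum runs from 2 to 14, giving 13 scores in steps of 100/12 = 8.33.
- Changes are k × 8.33. A change that meets 10 but not 15 would need k between 10/8.33 = 1.2 and 15/8.33 = 1.8. No integer lies there.
- If only one of the two items is answered, the score is a multiple of 16.67, which is on the same grid.

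**Enumeration of all 13 × 13 = 169 pairs of baseline and follow-up score.**
- 15 versus 10 points: 0 of 169 pairs change category.
- 5 versus 10 points: 24 of 169 change, namely the 12 one-step rises and the 12 one-step falls.
- Both counts are the same whether the threshold is applied as at least or as more than, and with one item missing.

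**Size of the looser check.** The SD of change is not given. Assume changes centred on zero, normal, rounded to the 8.33 grid, with SD 15, 20 or 25:

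| Assumed SD of change | Deteriorated at 5 points | At 10 points | At 15 points |
|---|---|---|---|
| 15 | 39% | 20% | 20% |
| 20 | 42% | 27% | 27% |
| 25 | 43% | 31% | 31% |

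**Other scales.** Smallest change that meets each threshold, all items answered:

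| Scale | Items | 5 | 10 | 15 |
|---|---|---|---|---|
| Global health/QoL | two, 7 levels | 8.33 | 16.67 | 16.67 |
| Appetite loss, shortness of breath | one, 4 levels | 33.33 | 33.33 | 33.33 |
| Pain | two, 4 levels (assumed) | 16.67 | 16.67 | 16.67 |
| Fatigue | three, 4 levels (assumed) | 11.11 | 11.11 | 22.22 |

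The single items classify identically at all three thresholds, and so does pain if it has two items. On fatigue, 15 differs from 10 in 18 of 100 pairs. The QLQ-LC13 scales were not worked through, because the documents do not reproduce that module's items.

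**The missing-form rule.** On global health/QoL every valid assessment has the same category at 10 and 15. Any difference between the 15-point and main results must therefore come from assessments without a valid score, which the main rule counts as deteriorated and the sensitivity rule classifies by reason.

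**The case against.** A reader might infer that the whole planned robustness check is empty. The documents do not support that. The 5-point threshold is a real check on the key scale. The area under the curve uses no threshold at all and so tests dependence on the cut-off directly. The post-discontinuation classification and the graph also remain, and Section 10.5.1 promises further sensitivity work on missing data.

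A reader might also infer that the 15-point result must reproduce the main result. It need not, because the bullet couples the thresholds with a different missing-form rule. If the two changes are run together, 15 points against the main analysis isolates missing-data handling on this scale, and 5 against 15 isolates the threshold. Both comparisons are informative to someone who knows the grid. The plan does not say that they are to be read this way.

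Nor is the 5-point check shown to be void on fatigue. If a three-item score is compared with one based on two answered items, changes of 5.56 are possible, which meet 5 but not 10. The item counts for fatigue and pain are in any case assumptions: Appendix E lists questions without assigning them to scales.

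That the 10-point rule selects changes of 16.67 or more is not an error. It is how any cut-off acts on a discrete scale. It does need to be stated, because readers will otherwise take the main analysis to count smaller changes.

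Finally, HRQoL is exploratory and outside the error control for DFS and OS. That stands and limits the weight of the point. It does not rescue a threshold that cannot reclassify anyone on the scale named as key.

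**Conclusion.** The point holds for the 15-point threshold on global health/QoL. It reclassifies 0 of 169 score pairs relative to 10 points, so the threshold check covers a looser definition (changes of 8.33 or more, 24 of 169 pairs) and never a stricter one. For appetite loss and shortness of breath, thresholds of 5, 10 and 15 coincide; for pain they coincide if it has two four-level items. A difference between the 15-point and main results on global health/QoL would reflect missing-form handling alone.

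The result for the key scale is exact, given an equally weighted mean of questions 29 and 30. The percentages in the working depend on the assumed distribution of change and only illustrate scale. Materiality is low: no stated figure is wrong, and no primary or secondary conclusion is affected.

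**What to change.** Amend the first sensitivity bullet of Section 10.5:

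- For global health/QoL, replace 15 points by a threshold that selects the next attainable change, for example 20 points, which means 25 or more. This is chosen because it can give a different answer; the documents offer no evidence that 25 points is a clinical benchmark. Keep 5 points as the looser check.
- State that on this scale the 10-point rule in effect requires a change of 16.67. The same applies to the 10-point criterion in the progression analysis of Section 10.5.2.
- Do not present threshold sensitivity for single items. Confirm the item counts of the multi-item scales from the scoring manual before choosing their thresholds.
- Run the reason-based reclassification of missing forms as a separate sensitivity analysis at the main threshold, so that each result has one cause.

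The cost is SAP wording and a few extra tables. The data are already planned: Section 10.4 provides for recording why a form was not completed.

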10.3 HRQoL instruments

Health related quality of life will be assessed with the EORTC Quality of Life Questionnaire (QLQ-C30) version 3. This instrument is composed of multi-item and single-item scales. These include five functional scales (physical, role, emotional, social, and cognitive), three symptom (fatigue, nausea and vomiting and pain) and a global health status/QoL scale and six single items (dyspnea, insomnia, appetite loss, constipation, diarrhea and financial difficulties). All scales and single items meet the standards for reliability. The reliability and validity of the questionnaire is highly consistent across different language-cultural groups [Ref. 76]. The average time to complete the questionnaire is approximately 10 minutes.

Additionally, the QLQ-LC13 lung cancer module to the QLQ-C30, which measures HRQoL relevant to specific symptoms (chest pain, cough and dyspnea) common in lung cancer will be included [Ref. 77]. The lung cancer module is meant for use among a wide range of lung cancer patients varying in disease stage and treatment modality. The module comprises 13 questions assessing lung cancer-associated symptoms (cough, haemoptysis, dyspnoea and site specific pain), treatment-related side effects (sore mouth, dysphagia, peripheral neuropathy and alopecia) and pain medication. The EORTC QLQ-C30 version 3 has been translated in over 50 languages according to a standardized translation procedure.

The domains of interest as specified in the previous paragraph are covered by the global health/QoL scale and the pain, fatigue appetite loss, shortness of breath, symptom scales of the QLQ-C30; and the cough, chest pain and dyspnea symptom scales of the QLQ-LC13.

EuroQol (EQ)-5D was developed to assess health outcomes from a wide variety of interventions on a common scale, for purposes of evaluation, allocation and monitoring [Ref. 78]. Index-based values ('utilities') facilitate the calculation of quality-adjusted life years (QALYs) that are used to inform economic evaluations of health care interventions. The EQ-5D-3L descriptive system comprises 5 dimensions: mobility, self-care, usual activities, pain/discomfort and anxiety/depression; each dimension has 3 levels: no problems, some problems, extreme problems. There are more than 100 official language versions of EQ-5D-3L.

English version of these HRQoL Instruments are included as protocol [Appendix E](#), with the list of validated versions available in other languages.

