- ◆ The change from baseline per time point will be displayed graphically.

These analyses will be repeated on the secondary HRQoL scales.

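### In the HRQoL AUC sensitivity analysis, scoring missing values as 0 is worst-case for global health but best-case for the symptom scales on which it appears to be repeated

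*Combined protocol and SAP*

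**What the plan says.** All points are in section 10.5 of the combined protocol and SAP unless noted.

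- **Main HRQoL analysis.** Change from baseline is classed as improved, stable or deteriorated at each time point. "Patients without a valid HRQoL outcome at a certain time will be considered as having deteriorated at that time".
- **AUC sensitivity analysis.** "The area-under-the-curve (AUC) will be calculated for each patient based on the global health/QoL scores. Missing values will be considered as 0".
- **Extension.** After the list of sensitivity analyses: "These analyses will be repeated on the secondary HRQoL scales". Secondary scales are not defined. The section otherwise speaks of one key endpoint (global health/QoL), supportive endpoints and other endpoints.
- **Supportive endpoints.** "pain, fatigue, appetite loss, shortness of breath, cough, chest pain and dyspnea symptom scales".
- **Scoring.** "All scales and single items are scored on categorical scales and linearly converted to 0-100 scales".
- **Item codes (Appendix E, QLQ-C30).** The global items, such as "How would you rate your overall health during the past week", run from 1 (very poor) to 7 (excellent). The symptom items, such as "Have you had pain", run from 1 (not at all) to 4 (very much).

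Section 10.5.1 on missing data gives no rule that changes the score assigned to a missing symptom value.

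**The concern.** A sensitivity analysis of missing data should put a different but interpretable assumption beside the main one. For global health/QoL the zero rule does so: it is harsh on missing visits, as the main analysis is. Carried over to symptom scales, the same zero rewards missing visits.

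If the main analysis and the AUC then disagreed on, say, fatigue, the reader could not tell whether the data are fragile or the two rules simply pull in opposite directions. The missing visits are also unlikely to be balanced, because the plan assumes OS hazard ratios of 0.6 to 0.765. If survival improves as assumed, deaths alone would make pembrolizumab's symptom AUC look worse and its global health AUC look better, from the same missing visits. With other patterns of missingness the bias could favour either arm.

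**Working it through.** **The plan's own figures.** The only HRQoL numbers stated are sample sizes, which are not in dispute. For 10 points with SD 20, a t-test calculation gives 64 per arm (128). For 15 points, the normal approximation gives 28 per arm (56). Both agree with the plan.

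**Direction of the scales.** Linear conversion of the Appendix E codes:
- Symptom item: (code − 1)/3 × 100, so 1, 2, 3, 4 become 0, 33.3, 66.7, 100. Zero is the best score.
- Global item: (code − 1)/6 × 100, so 1, 4, 7 become 0, 50, 100. Zero is the worst score.

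**Method for the size.** Trapezoid AUC over the section 10.4.1 visits (weeks 0, 12, 24, 36, 48, 74, 100, 152, 204, 256), divided by 256 to give an average score. Baseline is complete and carries weight 6/256 = 0.0234; the post-baseline visits carry 250/256 = 0.9766.

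**One patient.** Weeks 74 to 256 carry weight (26 + 39 + 52 + 52 + 26)/256 = 195/256 = 0.762. For a patient missing from week 74 onward:

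| Scale, constant true score | Complete | Missing = 0 | Missing = 100 |
|---|---|---|---|
| Symptom, 33.3 | 33.3 | 7.9 (looks better) | 84.1 (looks worse) |
| Global health, 66.7 | 66.7 | 15.9 (looks worse) | not applicable |

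The main analysis would count 5 of the 9 post-baseline visits as deteriorated on either scale.

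**Two arms, no true symptom difference.** The documents give no symptom means, missing rates or visible control-arm OS. Assumed: symptom mean μ of 25 to 35.

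1. *Flat gap of 10 percentage points at every post-baseline visit.* Shift = 0.10 × 0.9766 × μ = 2.44 (μ = 25) to 3.42 (μ = 35). The arm with more missing data looks better. With missing scored 100 instead, the shift is 0.10 × 0.9766 × (100 − μ) = 7.32 to 6.35 points against that arm.
2. *Gap growing linearly from 0 to 10 points at week 256.* The average gap is 0.05, so the shift is 0.05 × μ = 1.25 to 1.75. Scored 100, it is 3.75 to 3.25 the other way.
3. *Deaths only, all survivors answering, post-death visits treated as missing.* Exponential survival with S_pembrolizumab = S_control^HR, and assumed control 5-year OS of 50%, 60% or 70%. The shift is the time-averaged difference in the proportion alive, multiplied by μ.

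| OS HR (Protocol summary) | Difference in proportion alive (50/60/70%) | Pembrolizumab symptom AUC looks worse by |
|---|---|---|
| 0.765 (whole population) | 0.0539 / 0.0440 / 0.0335 | 0.0335 × 25 = 0.84 to 0.0539 × 35 = 1.89 |
| 0.60 (PD-L1 strong positive) | 0.0952 / 0.0769 / 0.0581 | 0.0581 × 25 = 1.45 to 0.0952 × 35 = 3.33 |

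With missing scored 100, the same deaths make pembrolizumab look better by 2.2 to 4.0 points (HR 0.765) and 3.8 to 7.1 points (HR 0.60).

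**The case against.** - **The AUC bullet names only global health/QoL, where zero is sound.** True: the conflict arises only through the sentence that repeats the analyses, and the term secondary is undefined. But that sentence covers the whole list without exception and supplies no other missing score. An analyst following the text would use 0; one who reversed it would be making an unplanned choice with data in hand.
- **Scale direction is inferred.** The EORTC scoring manual is cited but not supplied. For pain, fatigue, appetite loss and shortness of breath, the printed codes and the linear conversion make the inference firm. The items behind "the cough, chest pain and dyspnea symptom scales of the QLQ-LC13" are not printed, so the same direction is assumed there. The point stands on the QLQ-C30 scales alone.
- **The size rests on assumptions, including a horizon of week 256 that the plan does not state for the AUC.** This stands. Section 10.2 speaks of the treatment period and a limited follow-up. In scenario 3 the shift to week 100 is 0.4 to 0.9 points (HR 0.765) and 0.6 to 1.6 (HR 0.60); to week 48 it is 0.2 to 0.5 and 0.3 to 0.8. The sign does not change.
- **Other checks exist.** Sections 10.5 and 10.5.1 plan reclassification by reason for non-compliance and an examination of dropout, none of which uses zero. This limits the harm but does not make the AUC interpretable on symptom scales.
- **Scoring 100 shifts the result more.** Correct: it restores the direction but does not remove bias. That favours restricting the AUC to global health/QoL.

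**Conclusion.** The concern holds. Following the text, a missing visit takes the worst score in the global health AUC and the best score in the symptom AUC, and the latter runs against the main analysis. This rests on reading the secondary scales as the supportive symptom scales and, for the QLQ-LC13 scales, on an assumed direction.

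The illustrated shifts under the zero rule run from 0.8 to 3.4 points to week 256, all below the plan's 10-point threshold; a shorter horizon shrinks the deaths-only scenario further. They depend on assumed symptom means, missing rates and control survival, and are illustrative. The case for correcting the rule is its wrong direction, not the size of its effect. It cannot affect DFS, OS or the main HRQoL analysis.

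**What to change.** In section 10.5, name the scales on which each sensitivity analysis is repeated, replacing the undefined reference to secondary scales. Then do one of the following:

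1. **Preferred:** restrict the AUC to global health/QoL, where the zero rule has its intended meaning.
2. **If the symptom AUC is kept:** set missing values at the unfavourable end of each scale (0 for global health/QoL, 100 for symptom scales), or reverse-score the symptom scales before applying 0. Label the result a worst-case analysis, since it deliberately penalises the arm with more missing data and the shifts are larger (6.3 to 7.3 points in scenario 1).

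The cost is one sentence in the plan. A scale-direction flag in the analysis program is needed only under the second option.
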